2. RATIONALE	
3. THEORETICAL FRAMEWORK	
4. RESEARCH QUESTION/AIM(S)	
5. STUDY DESIGN/METHODS	
6. STUDY SETTING	
7. SAMPLE AND RECRUITMENT	
8. ETHICAL AND REGULATORY COMPLIANCE	
9. DISSEMINATION POLICY	
10. REFERENCES	
11. APPENDICES	

KEY STUDY CONTACTS

Chief Investigator	[name] Clinical Research Fellow Clinical Investigation and Research Unit Royal Sussex County Hospital [name] [contact] E-mail: [contact]
Study Co-ordinator	[name] Clinical Research Fellow Clinical Investigation and Research Unit Royal Sussex County Hospital [name] [contact] E-mail: [contact]
Sponsor	[name] Head of Research and Development Brighton and Sussex University Hospitals NHS Trust Research and Development Office [name] [contact] E-mail: [contact]
Joint-sponsor(s)/co-sponsor(s)	N/A
Funder(s)	Names and contact details of ALL organisations providing funding and/or support in kind for this study
Key Protocol Contributors	[name] Consultant Clinical Oncologist Sussex Cancer Centre [name] [contact] E-mail: [contact] [name] Consultant Clinical Oncologist The Royal Marsden Hospital [name]

	
[contact] E-mail: [contact]
 
[name] Professor of Clinical Oncology Institute of Cancer Sciences & Beatson West of Scotland Cancer Centre University of Glasgow [name] [contact] E-mail: [contact]
 
[name] The Walton Centre [name] [contact] E-mail: [contact]

--	--

STUDY SUMMARY

Study Title	B rain I maging to predict T oxicity in E lderly patients after R adiotherapy
Internal ref. no. (or short title)	BRITER study
Study Design	Observational cohort imaging study
Study Participants	Patients newly diagnosed with glioblastoma aged \geq 65 years undergoing radiotherapy treatment
Planned Size of Sample (if applicable)	100 patients
Follow up duration (if applicable)	6 months
Planned Study Period	2 years
Research Question/Aim(s)	Can you use MRI derived imaging parameters to predict the degree of side effects in patients receiving cranial radiotherapy as treatment for Glioblastoma Multiforme?

FUNDING AND SUPPORT IN KIND

FUNDER(S) (Names and contact details of ALL organisations providing funding and/or support in kind for this study)	FINANCIAL AND NON FINANCIAL SUPPORT GIVEN
Sussex Cancer Fund c/o [name] Royal Sussex County Hospital [name]	Funded the total cost of the study - £62,000

[figure not shown]

1 BACKGROUND

Glioblastoma (GBM) is the commonest primary malignant brain tumour among the adult population with approximately 2,000 new cases diagnosed in the UK per year. Incidence peaks in the 7th and 8th decades of life and as our global population ages, rates are increasing. Outcomes from this disease remain poor with median life expectancy in the range of 12-18 months, dropping to 3-6 months in the older populationⁱ. The reasons for this are multifactorial, including more aggressive tumour biology in the older age group, decreased tolerance to treatment related side effects and the potential of under treatment by doctors within the older age group.

Given the poor prognosis in this group, treatment must be balanced against side effects and worsening quality of life. In patients aged 65 or over there is a lack of consensus on standard of care. Radiotherapy has a survival advantage over best supportive careⁱⁱ however the optimal dose of radiotherapy is yet to be established^{iiiiiv}. A recent Phase III trial randomised elderly GBM patients to standard radiotherapy with 60Gy in 30#, hypofractionated radiotherapy of 34Gy in 10# or temozolomide (TMZ) chemotherapy alone. For patients older than 65, survival was significantly longer with TMZ or hypofractionated radiotherapy than with standard radiotherapy^{vi}. Those with defects in the DNA repair protein MGMT did significantly better in the chemotherapy arm than those with intact MGMT, a result which was replicated in the NOA-08 trial which randomised elderly GBM patients to standard radiotherapy with 60Gy in 30# or TMZ alone. This non-inferiority trial showed TMZ to be a suitable monotherapy option, with greater effect seen in those with MGMT promoter methylation^{vii}. Recently published evidence has shown a survival benefit from adding concomitant and adjuvant TMZ to a hypofractionated radiotherapy regime of 40Gy in 15# in patients aged over 65, again with greater effect seen in those with MGMT promoter methylation^{viii}. There is therefore now evidence to support the use of concomitant chemoradiotherapy or chemotherapy or radiotherapy as single agents amongst elderly GBM patients and an increasing interest in using MGMT promoter methylation status as a biomarker. However there remains a paucity of data surrounding the clinical and radiological basis by which individual patients are assessed for treatment.

The majority of GBM patients over 65 who are actively treated by oncologists receive some form of radiotherapy to the brain. Short term side effects from radiotherapy include fatigue, headache, cognitive defects, nausea, weakness and a need for increased steroid doses. Longer term side effects include persistent cognitive defects, long term fatigue and hormonal imbalances^{ix}. Radiation causes an inflammatory response within the brain tissue as well as disrupting the blood brain barrier. It affects the vasculature of the brain with endothelial cell damage leading to microvascular dilatation, thickening of the vessel wall and increased risk of microbleeds and ischemic strokes in the months to follow^x. There is a risk of inducing tissue necrosis from occlusion of small blood vessels within the brain parenchyma, leading to coagulation, focal necrosis and demyelination. Animal models have suggested radiation is cytotoxic to developing neuroglial progenitor cells with areas of stem cells such as the hippocampus and periventricular zones, particularly vulnerable to damage, leading to longer term neurocognitive decline^{xixii}. There is evidence to suggest that radiotherapy can stabilise or improve functional ability for some older patients with GBM aswell as providing a survival advantage however

clinical experience shows that the degree of side effects experienced and their impact on quality of life varies widely within this patient cohort.

Risk factors for toxicities from radiotherapy include dose, fractionation and age however we have no more accurate ways of predicting which patients are more likely to suffer side effects. MRI has been shown to accurately pick up microhaemorrhages and other ischemic changes which may correlate with a 'vulnerable' brain pre-treatment^{xiiixiv}. These MRI changes have been examined in Alzheimer and dementia research with correlations shown between MRI markers and disease severity^{xv}, however they have not yet been used within the neuro oncology setting.

We aim to examine the relationship between MRI markers of a 'vulnerable' brain and degree of acute side effects and change in quality of life amongst a population of older patients being treated with cranial radiotherapy for GBM.

2 RATIONALE

The poor prognosis of older GBM patients leads to an emphasis on the need for focusing on quality of life when deciding on treatment regimes. We have pathological markers which can help us determine sensitivity of the tumour to chemotherapy however we have no such guidance when it comes to making decisions about radiotherapy. If we were able to predict the degree of side effects likely to be experienced by a patient from radiotherapy treatment then it would enable us to make more individually tailored, patient centred treatment plans.

We aim to see if analysis of pre-radiotherapy MRI scans including T2 gradient echo and susceptibility weighted imaging sequences can correlate with acute treatment related toxicity and quality of life amongst patients aged 65 or over undergoing partial brain radiotherapy for GBM. As these patients have an average life expectancy of 3-6 months within the UK we are focussing on acute rather than long term side effects of radiotherapy.

MRI sequences will be utilised to determine any markers of background subclinical microvascular or degenerative disease in the normal brain including microhaemorrhage secondary to hypertension or cerebral amyloid angiopathy and atrophy with cortical volume measurement of the contralateral hemisphere. Additional susceptibility weighted sequences will be performed to identify the presence of microhaemorrhages in the contralateral normal-appearing brain parenchyma. These will be semi-quantitatively assessed using a modified established microhaemorrhage scoring methodology. Absolute measures of the contralateral normal-appearing hemisphere cortical volumes will be acquired using FSL freesurfer software and a volumetric T1 weighted acquisition. These techniques will give us a number of quantitative scores that can then be assessed for correlation with changes in quality of life and toxicity scoring systems.

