Baseline clinical assessment of the patients will be conducted in the NHS neuro-oncology outpatient clinic setting. These will involve the EORTC-QLQ-C30 quality of life questionnaire with the BN-20 brain and ELD14 elderly patient subsets of questions added, the MOCA questionnaire (please see Appendix for examples of these questionnaires) and a record of the amount of corticosteroid the patient is currently taking. The EORTC-QLQ-C30 quality of life questionnaires are designed to be completed by the patient (they are allowed to ask for help completing from family/carer) and could therefore be taken home by the patient or completed in the waiting room rather than being completed within the clinic. There is a risk of the questionnaires not being filled in and posted back if participants forget. We have costed for stamped addressed envelopes to be given to the patients in order to post the questionnaires back. The study team (who know the participant and would usually speak to them on the phone anyway during their treatment pathway) are able to call the participant to remind them to post back the questionnaires. The MOCA is administered by a member of the study team.

The original copies of these questionnaires will be in the CRF, alongside details of the participant's age, gender, comorbidities, treatment plan and social situation which will be recorded by the study team.

In most cases, the participant will have undergone an MRI scan as part of their usual care plan prior to attending the neuro-oncology clinic. If this scan has the required imaging sequences needed for the BRITER protocol then no further scanning is required. This will be assessed by the neuro oncology consultant during the outpatient clinic appointment or a member of the study team prior to the appointment. A list of the required sequences will be readily available for the study team during this process. If not all of the required sequences were completed then the patient will undergo a further MRI scan. This will be done prior to the participant starting radiotherapy treatment but should not delay the start of their radiotherapy treatment. Depending on local guidelines, this scan will either take place on the same site or may require travel to another site. Travel costs will be covered for the patient and carer to attend the extra MRI scan.

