- 3D volumetric inversion recovery or MP-RAGE (additional sequence - to allow accurate quantification of cortical thickness/volumes using Freesurfer software in addition to scoring methods of atrophy, must be acquired at 1mm or below)
- Axial T2* gradient echo (4mm slice thickness)

The scan thickness and sequences performed may vary slightly between sites however prior to opening the sites will confirm they can produce the necessary sequences for [name] to produce 5 quantitative scores (tumour volume, contralateral hemispheric brain volume, contralateral cerebral hemisphere cortical thickness, microhaemorrhage score and white matter hyperintensity score) from the images which reflect the degree of potential vulnerability of the brain to the side effects of radiotherapy. These will then be analysed in relation to the clinical questionnaires, steroid usage and grade 3-5 CTCAE radiotherapy toxicity score using SPSS. Multivariable logistic regression models will be fitted to look for significant ($P<0.05$) relationships between the 10 point change in EORTC QLQ quality of life questionnaires and the MRI parameters. Exploratory statistical analysis of the relationships between the MRI parameters and the secondary endpoints will be performed although the study is not powered to detect statistically significant relationships between these.

The creation of the database and statistical analysis of the results will be performed by the CI with the help of a research assistant.

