7.2 Sampling

7.2.1 Size of sample

Sample size calculations have been performed assuming a clinically significant end point of a 10 point change (SD=22.1 taken from the EORTC website reference guide) in EORTC QLQ questionnaire score between baseline and 8 weeks. Estimated sample size for one-sample comparison of proportion to hypothesized value assuming a 2 sided alpha of 0.05 and power of 0.9 gives a sample of

73. However, allowing for 20% attrition in questionnaire completion, this results in a sample size of 91. With 73 patients at 8 weeks, we will have 90% power for 5% significance to detect 5% of patients achieving a 10 point change in QoL. However, this small a proportion will only allow us to fit one variable in the model. It has therefore been recommended by the statistical team to aim for a recruitment target of 100 patients in order to fit the 5 MRI variables to the model.

Patients who are enrolled within CTIMP studies will not be eligible to be recruited into the study as they would introduce too many unknown variables for adequate statistical analysis with a cohort of this size.

Previous work done by this study group has shown this is a feasible recruitment target over 2 years.

The study team will review recruitment at 9 months and if it has not reached 25% then they will explore ways to increase recruitment, including opening at other sites.

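### Contralateral hemispheric brain volume enters the primary model with no stated scaling to head size, so this predictor mixes head size with atrophy

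*Combined protocol and SAP*

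**What the plan says.** Section 2 (Rationale) gives the purpose of the volumetric work as finding background disease in the normal brain, including "atrophy with cortical volume measurement of the contralateral hemisphere". It then states the method: "Absolute measures of the contralateral normal-appearing hemisphere cortical volumes will be acquired using FSL freesurfer software and a volumetric T1 weighted acquisition".

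Section 5 (Study design and methods) lists the five scores that the neuroradiologist will produce as indicators of vulnerability to radiotherapy: "tumour volume, contralateral hemispheric brain volume, contralateral cerebral hemisphere cortical thickness, microhaemorrhage score and white matter hyperintensity score". One sequence is requested "to allow accurate quantification of cortical thickness/volumes using Freesurfer software in addition to scoring methods of atrophy". Those atrophy scoring methods are not defined and are not among the five scores.

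The primary analysis in Section 5 is a multivariable logistic regression of the 10-point change on the MRI parameters, and no other covariate is named. The case report form does hold the questionnaires "alongside details of the participant's age, gender, comorbidities, treatment plan and social situation", so sex is recorded, but it is not assigned to the model. Section 7.2.1 sets the target: "aim for a recruitment target of 100 patients in order to fit the 5 MRI variables to the model".

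**The concern.** Atrophy is tissue lost relative to what was once there. One pre-treatment volume cannot show that loss without a reference for original size, because a small intact hemisphere and a larger atrophied one can give the same number. None of the other four scores measures head size, so the regression as described cannot remove it.

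Two things are at stake. First, a null result for volume could mean that the atrophy signal was diluted, and not that atrophy is unrelated to quality-of-life change. Second, a positive result could not be attributed cleanly to atrophy. Section 3 hopes to use the scan to identify patients for whom treatments other than radiotherapy would be better, so what this coefficient means matters.

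**Working it through.** The plan states no figure on this point, so there is none to reproduce. The check is a reading of the text followed by an illustration.

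**Step 1: the text.**
- Section 2 names cortical *volume* and calls the measures absolute.
- Section 5 names "contralateral hemispheric brain volume, contralateral cerebral hemisphere cortical thickness": a volume for the hemisphere and a *thickness* for the cortex. Cortical volume is not one of the five scores.
- No section mentions intracranial volume, head size, a brain fraction or any normalisation.
- No section names head size or sex as a covariate.

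The issue therefore bears on hemispheric volume, one of the five predictors. It extends to cortical volume only if that measure is used.

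**Step 2: what an unscaled volume contains.** Volume = head size × brain fraction, so log(volume) = log(head size) + log(brain fraction). If the two parts are independent, the variance of the log volume is the sum of the two variances.

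**Step 3: illustration from an assumed correlation.** Let r be the correlation of volume with head size (assumed 0.6 to 0.8; not in the documents).
- Share of variance due to head size = r²: 0.6² = 0.36 and 0.8² = 0.64.
- Correlation of volume with the brain fraction = √(1 − r²): √0.64 = 0.80 and √0.36 = 0.60.

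Any correlation between atrophy and outcome would be multiplied by 0.80 to 0.60, taking volume alone and assuming that head size is unrelated to the outcome.

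**Step 4: illustration from assumed spreads.** With coefficients of variation CVh for head size (assumed 6% to 12%) and CVa for brain fraction (assumed 3% to 10%), head-size share ≈ CVh² / (CVh² + CVa²).

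| CVh | CVa | Head-size share | Correlation with brain fraction |
|---|---|---|---|
| 6% | 10% | 0.0036 / 0.0136 = 26% | 0.86 |
| 8% | 7% | 0.0064 / 0.0113 = 57% | 0.66 |
| 10% | 5% | 0.0100 / 0.0125 = 80% | 0.45 |
| 12% | 3% | 0.0144 / 0.0153 = 94% | 0.24 |

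The range is wide because the documents give neither spread. The share is not trivial even at its lower end.

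**Step 5: what each remedy costs the model.** The target of 100 less the 20% attrition assumed in Section 7.2.1 leaves 100 × 0.80 = 80 evaluable patients for five MRI terms. Replacing volume by a fraction keeps five terms. Adding intracranial volume makes six, and adding sex as well makes seven.

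**The case against.** The strongest reply is that the plan never says a raw volume enters the regression. Section 2 applies the word absolute to cortical volumes only, in a sentence about acquisition. It follows a statement that microhaemorrhages will be rated semi-quantitatively, so the word may simply mean measured and not rated. For hemispheric volume, the lack of scaling is inferred from silence. This stands as a limit on the wording. It does not remove the gap: a predictor in the primary model needs a defined scale, and the only scale the protocol attaches to a volume is absolute.

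A reader might also infer more than the documents support:
- **That head size and sex, not atrophy, make up most of the predictor.** No document gives the spread of either component. The shares above rest on assumptions, and a share due to sex cannot be computed at all.
- **That sex differences in how quality of life is reported would appear as an MRI effect.** The primary outcome is a change from baseline, so stable differences in reporting largely cancel within a patient. Only a sex difference in the change itself would confound, and nothing in the documents indicates one.
- **That small healthy brains would be classed as vulnerable and large atrophied ones as robust.** The plan defines no cutoff, direction or composite score; each coefficient is estimated from the data.
- **That the study needs a known multiple of its sample size.** With the assumed r, 1/(1 − r²) runs from 1/0.64 = 1.56 to 1/0.36 = 2.78, but that result is for a single predictor. The planned model also holds cortical thickness, a second atrophy-type measure, so the loss within the five-term logistic model is not shown.

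**Conclusion.** The concern holds for one of the five primary predictors. As written, contralateral hemispheric volume has no stated scaling to head size and so mixes head size with the atrophy it is meant to help capture. That would dilute any association between atrophy and quality-of-life change.

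The direction follows from the definition of a volume, provided that head size is not itself related to the outcome. The amount is unknown; 36% to 64% of variance is an illustration that depends on the assumed correlation. The other four scores are not affected. This change should be made before analysis because it is inexpensive and gives a better-defined predictor. It does not undermine the study as a whole.

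**What to change.** - **Scale the volume.** State in Section 5 that contralateral hemispheric volume enters the model as a fraction of intracranial volume estimated from the same volumetric T1. Treat cortical volume the same way if it is used.
- **Prefer the fraction to a covariate.** An intracranial-volume covariate would also deal with head size, but it adds a term to a model whose sample was set for five MRI variables. Section 7.2.1 itself warns that a low proportion of patients with the outcome would support only one variable.
- **Leave cortical thickness unscaled.**
- **Reconcile Sections 2 and 5.** Say whether the cortical predictor is volume or thickness, and whether the atrophy scoring methods mentioned in Section 5 enter any analysis.

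Cost: no new scan, since the volumetric T1 and the Freesurfer processing are already planned, and one further measurement per patient from the same images. The downside is a visual check of the intracranial segmentation where tumour distorts it.

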3 THEORETICAL FRAMEWORK

Older patient with a GBM have an average prognosis of 3-6 months. Treatment options are universally palliative and should be aimed at improving or maintaining quality of life for the remainder of these patients' lives. Treatment decisions therefore need to be based around an informed conversation with the patient of the balance between survival benefit and side effect profile. Clinical trials have shown

efficacy of single agent radiotherapy or chemotherapy or short courses of concurrent chemoradiation. Molecular markers have been developed which can help guide decisions regarding the likely efficacy of chemotherapy however no such marker exist for decisions regarding radiotherapy.

Radiotherapy is an effective palliative treatment for GBMs and has been shown in clinical trials to maintain or improve health related quality of life. However outside of a clinical trial population, usual clinical practice reveals some patients in whom the side effect profile from cranial radiotherapy is intolerable and has a significant detrimental effect on patients' quality of life for their remaining short lifespan. The BRITER study aims to examine whether analysis of pre-treatment MRI scans in this cohort could help to predict who is more vulnerable to these side effects and therefore reveal a group of patients in whom single agent chemotherapy or best supportive care would be better treatment options.

